### **6.8. Dosing Instructions**

Patients will be instructed to take their assigned SEL24/MEN1703 dose at regular intervals in the morning on dosing days, swallowed with water or an alternative drink. Doses shall be taken on an empty stomach (at least 2 hours after and 1 hour before eating). Patients will be asked to record the exact time they take each dose, how many capsules they take, what they have eaten and drunk, and when, before and after each dose in their dosing diary (see [Section 6.6](#)). Patients enrolled once the DMC has approved the introduction of the formulated SEL24/MEN1703 will be instructed to take the assigned number of capsules, following the same dosing instructions.

Patients will be instructed not to make up missed doses or vomited doses. Full details of dosing instructions will be provided to patients in the PIS.

Patients must be informed that a SEL24/MEN1703 photosensitivity/phototoxicity effect cannot be excluded. For this reason, patients should minimize or avoid exposure to natural or artificial sunlight (tanning beds or UVA/B treatment) during the entire study period. If patients need to be outdoors when taking SEL24/MEN1703, they should wear loose-fitting clothes that protect skin from sun exposure and discuss other sun protection measures with the investigator. If a sunburn like reaction or skin eruption occurs, patients should contact the investigator.

## 6.9. Permitted and Restricted Concomitant Medications

Medications specifically prohibited in the exclusion criteria ([Section 3.2](#)) are not allowed during the ongoing study. If there is a clinical indication for any medication specifically prohibited during the study, discontinuation from study therapy may be required. The Investigator should discuss any questions regarding this with the assigned Medical Monitor for the study. The final decision on any supportive therapy or vaccination rests with the Investigator and/or the patient's primary physician. However, the decision to continue the patient on study treatment requires agreement from the Medical Monitor.

Note that use of erythropoiesis stimulating agents and growth factors during Cycle 1 is prohibited. Beyond Cycle 1, their use should be avoided; however, their use may be discussed with the Medical Monitor on a case-by-case basis.

### 6.9.1. Acceptable concomitant medications

All treatments that the Investigator considers necessary for their patient's welfare may be administered at their discretion in keeping with the standards of medical care. All concomitant medication will be recorded on the eCRF including all prescription, over-the-counter, herbal supplements, pre-medications, intravenous medications or transfusions. Note that the assessment of red cell transfusions will be part of the disease assessment criteria (see [Section 5.3.11](#)). If changes occur during the study period, documentation of drug dosage, frequency, route, and date may also be included on the eCRF. All concomitant medications the patient received within 30 days before the first dose of SEL24/MEN1703 and 30 days after the last dose of SEL24/MEN1703 should be recorded. Concomitant medications administered after 30 days from the last dose of SEL24/MEN1703 should be recorded for SAEs and any Events of Clinical Interest (ECIs) as defined in [Section 7.10](#).

Sites should follow their institutional guidelines for treating hypophosphatemia, including administration of oral or I.V. phosphate supplements. Phosphate supplements should be started the same day any  $\geq$ Grade 3 hypophosphatemia is detected. Patients should be retested no less than every 24 hours, until phosphate levels are  $\leq$ Grade 2. SEL24/MEN1703 treatment may be reinstated per the retreatment guidelines provided in [Section 4.4](#). Lower grade abnormalities should be monitored and corrected as soon as possible. Additional assessments should be carried out as clinically indicated.

### 6.9.2. Antibacterial and antifungal prophylaxis

Patients with grade 4 neutropenia should receive both antibacterial and antifungal prophylaxis according to institutional guidelines, as long as grade 4 neutropenia persists. Commonly used prophylactic agents (fluoroquinolones, azoles), with the exception of isavuconazole (not allowed, being a BCRP inhibitor) are not contraindicated, however careful clinical monitoring is recommended pending the clinical evaluation of potential for drug-drug interactions.

### 6.9.3. Potential for drug-drug interactions

Non-clinical drug interaction studies indicate that SEL24/MEN1703 may inhibit CYP2D6, and act as a substrate for CYP2D6 and BCRP. Between discontinuation of the following agents and the first administration of SEL24/MEN1703 (see [Exclusion Criterion 16](#)), a 7-day washout period, or a period corresponding to 4-5 half-lives of the agents, is therefore mandated:

- sensitive CYP2D6 substrates
- CYP2D6 substrates with a narrow therapeutic range
- strong or moderate CYP2D6 inhibitors
- BCRP inhibitors

In addition, any drug which is a CYP2D6 substrate, a strong or moderate inhibitor of CYP2D6, or a BCRP inhibitor should not be administered concomitantly with SEL24/MEN1703 during the study. If a patient requires a drug in these categories, the Investigator should explore the use of an alternative therapeutic treatment/agent. If this is not possible, SEL24/MEN1703 should be discontinued and a 7 day washout period allowed before administration of the required therapeutic agent commences. Following discontinuation of SEL24/MEN1703 for this reason, treatment with SEL24/MEN1703 cannot re-start once treatment with the CYP2D6 substrate, or inhibitor of CYP2D6 or BCRP has stopped. Examples of relevant drugs to consider are provided below.

#### CYP2D6 substrates:

- Sensitive CYP2D6 substrates: atomoxetine, desipramine, dextromethorphan, metoprolol, nebivolol, perphenazine, thioridazine, tolterodine, venlafaxine, nortriptyline
- CYP2D6 substrate with narrow therapeutic range: thioridazine

#### CYP2D6 inhibitors:

- Strong CYP2D6 inhibitors: quinidine, fluoxetine, paroxetine, bupropion, dacomitinib, ecstasy, terbinafine
- Moderate CYP2D6 inhibitors: AMD070, cinacalcet, moclobemide, mirabegron, duloxetine, dronedarone, eliglustat, tipranavir/ritonavir, fluvoxamine, cimetidine

#### BCRP inhibitors:

- Representative BCRP inhibitors: cyclosporine, elacridar (GF120918), eltrombopag, gefitinib, curcumin, isavuconazole

Please refer to [Appendix F](#) for a (not-exhaustive) list of CYP2D6 substrates, CYP2D6 inhibitors and BCRP inhibitors.

## 7. ADVERSE EVENTS AND REPORTING REQUIREMENTS

### 7.1. Assessment of Safety

All patients who have received at least one dose of SEL24/MEN1703 will be considered evaluable for safety. All AEs and SAEs will be collected from the time the patient gives informed consent up to and including the 30 day follow up (Final Study Visit). There will be a baseline medical condition review taken at Screening. Events, other than the primary disease under evaluation, that worsen in severity or frequency from this baseline assessment during the study, should be recorded and reported as AEs.

### 7.2. Adverse Event Definition

An AE is defined as any new untoward medical occurrence or worsening of a pre-existing medical condition in a patient or clinical investigation patient administered a medicinal product and which does not necessarily have a causal relationship with this treatment. An AE can therefore be any unfavorable and unintended sign (including a clinically significant abnormal laboratory finding, for example), symptom, or disease temporally associated with the use of a medicinal (investigational) product, whether or not considered related to the IMP.

The definition covers also medication errors and uses outside what was foreseen in the protocol, including misuse and abuse of the product (see chapter 7.7.2).

Adverse events include:

- worsening (change in nature, severity, or frequency) of conditions present at the start of the study;
- intercurrent illness;
- drug interactions;
- experiences related or possibly related to concomitant medications;
- clinically significant abnormal laboratory values or shifts from baseline; and
- clinically significant abnormalities in physical examination, vital signs, weight, or ECG.

The Investigator must record all the available information concerning any non-serious AE (whether or not deemed related to the study treatment) in the corresponding section of the eCRF-AE pages, within 5 calendar days after the first knowledge of the occurrence of the event

Progression of the disease under study (i.e. AML) will not be captured as an AE.

Surgical procedures or other therapeutic interventions themselves are not AEs, but the condition for which the surgery/intervention is required is an AE and should be documented accordingly.

Planned surgical measures and the condition(s) leading to these measures are not AEs, if the condition(s) was (were) known before the period of observation and did not worsen during study. In the latter case, the condition should be reported as medical history.

### 7.3. Importance of Adverse Event Reporting

Timely and complete reporting of safety information is very important to assist in the identification of any untoward medical occurrence, thereby ensuring:

- the safety of study patients;
- a greater understanding of the overall safety profile of the investigational drug;
- recognition of any dose-related investigational drug toxicity;
- appropriate modification of study protocols;
- improvements in study design or procedures as required; and
- adherence to required ethical and regulatory requirements for clinical study conduct.

### 7.4. Evaluating Adverse Events

Following the patient's written consent to participate in the study, all AEs should be collected. All identified AEs must be recorded and described on the appropriate AE page of the eCRF, except for those events occurring prior to the first dose of study medication, which should be recorded on the Medical History eCRF page (unless related to the study procedures performed prior to dosing ; in this case they have to be reported as an AE). Where known, the diagnosis of illness or disorder should be recorded, rather than listing individual symptoms.

The following information should be captured for all AEs: date of onset and resolution, severity of the event (see definitions in [Section 7.5](#)), assessment whether the event was serious or non-serious, Investigator's opinion of the relationship to IMP (see definitions in [Section 7.8](#)) treatment required for the AE, action taken with IMP, and information regarding resolution/outcome.

### 7.5. Severity

All AEs (including SAEs) are to be accurately recorded on the AE page of the patient's eCRF. Each event will be graded for severity using the classifications of NCI CTCAE v4.03 (see [Appendix C](#)). For events not addressed in the NCI CTCAE v4.03, classifications the following grading will apply:

- **Mild (Grade 1)** - Mild; asymptomatic or mild symptoms; clinical or diagnostic observations only; intervention not indicated.
- **Moderate (Grade 2)** - Moderate; minimal, local or noninvasive intervention indicated; limiting age-appropriate instrumental activity of daily living.
- **Severe (Grade 3)** - Severe or medically significant but not immediately life-threatening; hospitalization or prolongation of hospitalization indicated; disabling; limiting self-care activity of daily living.
- **Life-threatening (Grade 4)** - Life-threatening consequences; urgent intervention indicated.
- **Death (Grade 5)** - Related to adverse event.

### 7.6. Serious Adverse Events

An SAE is defined as any untoward medical occurrence that at any dose causes or qualifies as the following:

- Results in death.
- Is life-threatening:
  - “Life-threatening” means that the patient was at immediate risk of death at the time of the SAE; it does not refer to an SAE that hypothetically might have caused death if it were more severe.
- Requires hospitalization or prolongation of existing hospitalization:
  - This means that hospital inpatient admission or prolongations of hospital stay were required for the treatment of the SAE or that they occurred as a consequence of the event.
  - Visits to a hospital by ambulance or to the emergency room without admission will not be regarded as hospitalization unless the event fulfills any other of the serious criteria.
- Results in persistent or significant disability or incapacity:
  - “Persistent or significant disability or incapacity” means a permanent or significant and substantial disruption of a person’s ability to carry out normal life functions.
- Is a congenital anomaly or birth defect.
- Is an important medical event:
  - Medical and scientific judgment should be exercised in deciding whether expedited reporting is appropriate in situations where none of the outcomes listed above occurred. Important medical events that may not be immediately life-threatening or result in death or hospitalization but may jeopardize the patient or may require intervention to prevent one of the other outcomes listed in the definition above should also usually be considered serious. Examples of such events include allergic bronchospasm requiring intensive treatment in an emergency room or at home, blood dyscrasias, or convulsions that do not result in inpatient hospitalization, or the development of drug dependency or drug abuse.

**Note-1:** These characteristics/consequences have to be considered at the time the event occurs. For example, regarding a life-threatening event, this refers to an event in which the subject was at risk of death at the time of the event; it does not refer to an event which hypothetically might have caused death if it were more severe.

Any other AE/ADR which is not included in the above definitions will be considered as non serious.

**Note-2:** Hospitalization lasting less than 24 hours or pre-planned hospitalization for diagnostic procedures or medical intervention shall not qualify as SAE.

For the purposes of this study, specified events considered to be expected in this patient population and during leukemia therapy will not require to be reported as SAEs (see [Section 7.6.1](#)).

All patients with SAEs must be followed up for outcome until it is considered resolved, returns to baseline, is chronically ongoing, stabilized, or is otherwise explained by the Investigator.

If the Investigator detects a SAE in a study patient after the end of the period of observation and considers the event possibly related to prior study treatment or procedures, they should immediately (within 24 hours of awareness) contact the Sponsor to determine how this event should be documented and reported. For screening failure patients, SAEs detected after SF declaration will be recorded only if the event is considered as possibly related to study procedures.

### 7.6.1. Exceptions to SAE reporting

For this study, the following events will be considered to be expected events in this population and during leukemia therapy other than SEL24/MEN1703 (e.g. myelosuppression and events secondary to disease) and should not be reported to the Sponsor as serious events unless the Investigator considers any of these events to be clinically concerning and of unusual manifestation with regard to severity, duration, frequency, outcome or other characteristics of the event. It is important to note that these events (with the exception of progression of AML), still need to be captured as AEs on the AE eCRF and will be reviewed by the DMC in aggregate with all cumulative safety data.

Expected events during leukemia therapy are:

- Myelosuppression due to disease or leukemia therapy :
  - febrile or infection episodes.
  - epistaxis or bleeding except for catastrophic CNS or pulmonary hemorrhage.
  - anemia, neutropenia, lymphopenia, thrombocytopenia, leukopenia, leukocytosis.
- Events due to underlying disease:
  - symptoms associated with anemia:
    - ~ fatigue.
    - ~ weakness.
    - ~ shortness of breath.
  - electrolyte abnormalities (sodium, potassium, bicarbonate, CO2, magnesium).
  - chemistry abnormalities (LDH, phosphorus, calcium, BUN, protein, albumin, uric acid, alkaline phosphatase, glucose).
  - coagulation abnormalities.
  - disease specific therapy (induction, maintenance, salvage, or stem cell therapy).
  - alopecia.
  - bone, joint, or muscle pain.
  - liver function test abnormalities associated with infection or disease progression.
  - disease progression.
- General therapy events:
  - events attributed to the use, placement and/or insertion of catheters.
  - renal failure associated with tumor lysis syndrome or antibiotic/antifungal therapy.

- rash due to antibiotic use.
- Hospitalization for the management of any of the above expected events.

Abnormal hematologic or clinical chemistry values, not considered to be clinically significant, will not be recorded on the adverse event eCRF, although all values will be recorded on the hematology and clinical chemistry laboratory eCRFs.

### **7.7. Other Important Events for Immediate Reporting**

In addition to the above criteria, AEs meeting either of the below criteria, although not serious per ICH definition, are reportable to the Sponsor in the same timeframe as SAEs to meet certain local requirements and the study needs.

- a new cancer (that is not a condition of the study);
- a reported pregnancy or lactation after receipt of study treatment and for up to 30 days from last dose;
- an overdose (defined as any dose of SEL24/MEN1703 which is more than the assigned dose for that patient); or
- an AE which qualifies as a DLT during Cycle 1 for patients in Part 1 (see [Section 7.7.3](#)).

Such events must be reported within 24 hours to the Sponsor via the eCRF. Once the information is saved in the eCRF, a notification e-mail will be automatically generated and sent to the Sponsor's Study Drug Safety Unit (SDSU). Only in case of breakdown of the eCRF System, the specific paper report form, provided to the sites, will be used. In such case, the Investigator will be responsible for sending the corresponding paper form and inserting the data in eCRF as soon as the system works again. The reporting procedures can be found in the *SAE report form completion manual* distributed to the sites.

#### **7.7.1. Exposure during pregnancy or lactation**

Although pregnancy and lactation are not considered AEs, it is the responsibility of Investigators or their designees to report any pregnancy or lactation in a patient (spontaneously reported to them) or pregnancy in a patient's partner that occurs during the study.

Pregnancies and lactations that occur in patients after the ICF is signed but before starting study treatment must be reported by the Investigator if they cause the patient to be excluded from the study. Pregnancies and lactations that occur in a study patient or a pregnancy in a patient's partner from the time of first study treatment through to 30 days following cessation of SEL24/MEN1703 study treatment must be reported by the Investigator. All reported pregnancies must be followed to the completion or termination of the pregnancy. If the pregnancy continues to term, the outcome (health of infant) must also be reported.

Such events must be reported within 24 hours to the Sponsor.

Pregnancy and lactation will be reported to the Sponsor via EDC. ONLY if the eCRF system does not work, the specific paper report form (Pregnancy Exposure Report form) will be completed and sent to the Sponsor by email or fax (see [Section 7.7](#)). The “Pregnancy Exposure Report” form will be distributed to the sites to be used for this purpose. The outcome of the reported pregnancies will be always notified to the Sponsor using the Pregnancy Exposure Report form. If the pregnancy results in an abnormal outcome (miscarriage or new-born with congenital abnormality and/or stillbirth), this will be recorded in the eCRF as a SAE and managed as described in [Section 7.10](#). The reporting procedures can be found in the *SAE report form completion manual* distributed to the sites.

#### 7.7.2. Misuse and overdose

Both misuse and overdose issues should be reported to the Sponsor’s SDSU within the same timelines as a SAE, even if they may not result in an adverse outcome (see [Section 7.7](#)). In the event of overdose, the patient should be observed closely for signs of toxicity. Appropriate supportive treatment should be provided if clinically indicated.

For the purpose of this protocol, an overdose is any dose of SEL24/MEN1703 which is more than the assigned dose level for that patient. The corresponding information should be entered on the overdose page in the eCRF no later than 24 hours of awareness by the site. Once the page is completed and saved by the staff involved in the study, an alert notification will be automatically sent to the Sponsor. ONLY if the eCRF system does not work or if the eCRF is not available, the paper CRF-AE report form shall be used and sent to the Sponsor by email.

The reporting procedures are described in detail in the *SAE report form completion manual* distributed to the sites.

In addition, if an AE (serious or non-serious) is associated with an overdose, it will be recorded on the AE page in the e-CRF, recording the overdose details.

If the pharmacy discovers that an overdose has or may have been administered, they should immediately contact the Investigator and Sponsor (or their delegate).

#### 7.7.3. Dose limiting toxicity

DLT events for dose escalation decisions will be assessed at the end of Cycle 1 (and on Day 42 in the case of protracted neutropenia in the absence of active AML), for each patient in each cohort and should be reported within 24 hours of the Investigator or their study team first becoming aware of the event. The AEs listed below will be considered as DLT unless they are clearly and incontrovertibly attributable to the underlying disease or to an extraneous cause:

- Grade 5 toxicity
- Grade 4 neutropenia lasting  $\geq 42$  days from the start of the therapy cycle in absence of evidence of active AML (<5% blasts)
- Grade 3 or 4 non-hematologic toxicity, except:
  - Alopecia;
  - Grade 3 fatigue, asthenia, anorexia, fever, or constipation;

- Grade 3 nausea, vomiting, or diarrhea not requiring tube feeding, TPN, or hospitalization;
- Infection, bleeding, or other expected direct complications of cytopenias due to active leukemia;
- Grade 3 or 4 electrolyte imbalances that respond to correction i.e. return to  $\leq$ Grade 2, within 48 hours (h) from correction's onset;
- Grade 3 increase in aspartate aminotransferase (AST) and/or, alanine aminotransferase (ALT) and/or alkaline phosphatase (ALP) recovering  $\leq$ Grade 2 within 7 days.

Only **clinically significant** abnormalities in laboratory findings, physical examination, vital signs, weight or ECG (see [Section 7.2](#)) will be considered for DLT assessment, according to the protocol definition.

#### 7.7.4. Investigational product complaints

Pharmaceutical technical complaints associated with the investigational product must be reported to the Sponsor immediately. The same reporting timelines as for SAEs apply.

### 7.8. Relationship

All AEs (including SAEs) will be assessed for the relationship of the AE to the study drug using the following standard definitions (for DLT events assessment for dose escalation decision please specifically refer to the above chapter 7.7.3):

- **Not Related:** The event or laboratory test abnormality (AE), with a time to drug intake with an unreasonable relationship and or non-plausibility and/or the existence of a clear alternative explanation.
- **Unlikely related** - The event or laboratory test abnormality (AE), with a time to drug intake that makes a relationship improbable (but not impossible). Disease or other drugs provide plausible explanations.
- **Possibly related** - The event or laboratory test abnormality (AE) has a reasonable time relationship to the drug intake, but it could also be explained by disease or other drugs. Information on drug withdrawal (dechallenge) may be lacking or unclear.
- **Probably related** - The event or laboratory test abnormality (AE) has a reasonable time relationship to the drug intake, it is unlikely to be attributed to a concurrent disease or other drugs and it follows a clinically reasonable response on withdrawal (dechallenge). Rechallenge (AE reappearance after drug reintroduction) is not required to fulfil this definition.
- **Definitely related** - The event or laboratory test abnormality (AE) has a plausible time relationship to the drug intake and it cannot be explained by a concurrent disease or other drugs. The response to withdrawal of the drug (dechallenge) should be plausible (pharmacologically, pathologically). The event must be definitive pharmacologically or phenomenologically (i.e. an objective and specific medical disorder or a recognised pharmacological phenomenon), using a satisfactory rechallenge procedure if necessary.

Please also refer to supporting information provided in [Appendix C](#). The relationship of the study treatment to an AE will be determined by the Investigator and subsequently reviewed by the Medical Monitor.

For reporting and data analysis purposes, AEs reported with a causality assessment of “Definitely”, “Probably”, and “Possibly” are to be considered as “having a reasonable causal relationship” to study drug. In case of disagreement between the Investigator and the Sponsor’s Medical Monitor, the more conservative assessment will determine the reportability of the case.

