### 1.5. Safety Guidance Information for Investigators

Throughout the study, Investigators should refer to the current edition of the Investigator's Brochure (IB) for a full review of the potential risks associated with treatment with SEL24/MEN1703 and details of expected AEs.

Based on available safety data, administration of SEL24/MEN1703 may be associated with the potential risk of **fatal thrombosis** and **severe hepatotoxicity**. In addition, hypophosphatemia has occurred at the 25, 50, 75, and 150 mg dose levels. Please refer to [Section 6.9.1](#) for further guidance on the management of this latter event.

No other particular risks have been identified for SEL24/MEN1703 according to available clinical data. Nevertheless, results from non-clinical data do not allow to exclude the potential phototoxic effect of MEN1703. To this end, new safety measures - Inclusion of photosensitivity/phototoxicity

preventive measures – have been implemented in previous Clinical Trial Protocol Versions 11.2 and 11.3. Please refer to [Section 6.8](#) for further guidance on the prevention and management of this event.

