## APPENDIX C: SUPPORTING INFORMATION FOR ASSESSMENT OF ADVERSE EVENTS

National Cancer Institute Common Terminology Criteria for Adverse Events (NCI CTCAE) v4.03 can be found at the website of the National Cancer Institute.

<http://evs.nci.nih.gov/ftp1/CTCAE>

The following table provides supporting information to assess the relationship of AEs with study (test) drug.

1	Not related	This category applies to those adverse events which, after careful consideration, are clearly and incontrovertibly due to extraneous causes (disease, environment, etc.).
2	Unlikely (must have two)	In general, this category can be considered applicable to those adverse events which, after careful medical consideration at the time they are evaluated, are judged to be unrelated to the test drug. An adverse event may be considered unlikely if or when: 
 
1. It does not follow a reasonable temporal sequence from administration of the test drug.
 
2. It could readily have been produced by the patient's clinical state, environmental or toxic factors, or other modes of therapy administered to the patient.
 
3. It does not follow a known pattern of response to the test drug.
 
4. It does not reappear or worsen when the drug is readministered.
 

3	Possibly (must have two)	This category applies to those adverse events for which, after careful medical consideration at the time they are evaluated, a connection with the test drug administration appears unlikely but cannot be ruled out with certainty. An adverse event may be considered possibly related if or when: 
 
1. It follows a reasonable temporal sequence from administration of the test drug.
 
2. It could not readily have been produced by the patient's clinical state, environmental or toxic factors, or other modes of therapy administered to the patient.
 
3. It follows a known pattern of response to the test drug.
 

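### Appendix C's causality counts conflict with Protocol 7.8: a well-timed AE that disease could readily explain may be coded 'Unlikely' instead of 'Possibly related' and leave the related-AE tables

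*Protocol*

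**What the plan says.** Protocol 7.8 sets the scale: "All AEs (including SAEs) will be assessed for the relationship of the AE to the study drug using the following standard definitions". Three of its five categories matter here.

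- **Possibly related:** the event "has a reasonable time relationship to the drug intake, but it could also be explained by disease or other drugs". Nothing is said about a known drug pattern.
- **Unlikely related:** an event "with a time to drug intake that makes a relationship improbable (but not impossible"), with disease or other drugs as plausible explanations.
- **Not related:** unreasonable timing, non-plausibility, or a clear alternative explanation.

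The section then sends the assessor to Appendix C for supporting information. SAP 7.2.2 repeats both the definitions and that reference.

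Appendix C sets thresholds by count. 'Possibly' needs two of three criteria: reasonable timing; "It could not readily have been produced by the patient's clinical state, environmental or toxic factors" (or other therapy); and a known pattern of response. Its opening sentence says that "a connection with the test drug administration appears unlikely but cannot be ruled out with certainty". 'Unlikely' needs two of four: no reasonable timing; the clinical state could readily have produced the event; "It does not follow a known pattern of response to the test drug"; and no reappearance or worsening on readministration. Its opening sentence says that such events "are judged to be unrelated to the test drug".

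Protocol 7.8 counts 'Definitely', 'Probably' and 'Possibly' as causally related for reporting and analysis. SAP 11.5.2 builds its binary related variable from the same three, plus events with missing causality. 'Unlikely' falls outside.

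**The concern.** On the question of an alternative explanation, the two texts point in opposite directions. In 7.8, a possible role for disease is part of what makes a well-timed event 'Possibly related'. In Appendix C, a ready explanation by disease counts against 'Possibly' and towards 'Unlikely'. Timing, which defines 'Unlikely' in 7.8, is only one of four interchangeable criteria in Appendix C.

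The boundary between these two categories is also the boundary of the related flag. That flag feeds the related-AE tables, the serious-and-related tables, the table of related deaths, and the related rows of the AE overview. These outputs are part of how the Part 2 safety objective will be described.

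The event type at issue could occur in this trial. Protocol 1.5 names thrombosis, hepatotoxicity and hypophosphatemia as risks and adds: "No other particular risks have been identified for SEL24/MEN1703 according to available clinical data". Many events will therefore have no recognised drug pattern, although the Investigator's Brochure may list more. Protocol 7.6.1 lists events commonly due to AML, such as fatigue, weakness and bone pain, and requires that they still be recorded as AEs. A criterion that counts the absence of a known pattern against relatedness works poorly for a drug whose pattern is still being learned.

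**Working it through.** The plan gives no figure to reproduce. The check applies both rule sets to the same events.

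**Step 1. The set of events.** Timing is reasonable. Disease or another drug is a possible but not clear explanation, and a drug link is not judged non-plausible. Section 7.8 then rules out 'Not related' and 'Unlikely', and the event is at least 'Possibly', hence related.

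**Step 2. Appendix C scores.** For each event:

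- 'Possibly' score = reasonable timing + not readily produced by clinical state + known pattern (2 of 3 needed).
- 'Unlikely' score = no reasonable timing + readily produced + no known pattern + no recurrence on readministration (2 of 4 needed). The last item is left unscored, because no text says that a routine further cycle counts as readministration.

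| Readily produced by disease | Known drug pattern | 'Possibly' score | 'Unlikely' score | Category by count |
|---|---|---|---|---|
| yes | yes | 1+0+1 = 2 | 0+1+0 = 1 | Possibly |
| yes | no | 1+0+0 = 1 | 0+1+1 = 2 | Unlikely |
| no | yes | 1+1+1 = 3 | 0+0+0 = 0 | Possibly |
| no | no | 1+1+0 = 2 | 0+0+1 = 1 | Possibly |

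One of the four combinations departs from 7.8. These are combinations of rules and say nothing about how often such events occur.

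**Step 3. Readministration.** If the event does not recur, the 'Unlikely' score in row 2 rises from 2 to 3. If it recurs or was not tested, the score stays at 2. 'Possibly' stays at 1 throughout, so the conflict does not depend on this item.

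**Step 4. Could a higher category rescue row 2?** Appendix C's 'Probably' needs three of four: timing, not reasonably explained by the patient's state, improvement on stopping or reducing the drug, and known pattern. Row 2 can reach at most 1+0+1+0 = 2. 'Definitely' needs all its criteria. By count, no related category is open.

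**Step 5. Where the flag is used.** SAP 13.2.1 lists Tables 2.2.1, 2.2.2, 2.2.2.1, 2.2.2.2, 2.2.3, 2.2.4 and 2.2.5 (7), Tables 2.4.1 to 2.4.5 (5), and Table 2.5.3 (1): 7 + 5 + 1 = 13. A single event enters only those for which it qualifies by grade, seriousness, action taken or outcome.

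**Step 6. Size per patient.** If the recoded event is the patient's only related event in a row, that row changes by 1/23 = 4.3 percentage points in the all-comers cohort and by about 1/20 = 5.0 points in the IDH-mutant cohort.

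**The case against.** The strongest reply is that the hierarchy is already visible. Section 7.8 gives the definitions to be used for all AEs, Appendix C is labelled supporting information, and SAP 7.2.2 reproduces only the 7.8 definitions. Appendix C is also phrased permissively: an event meeting two criteria *may* be considered unlikely. Its opening sentence for 'Possibly' fits the event in row 2. An assessor guided by that sentence, or by 7.8, reaches 'Possibly'.

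Most of this stands, and it limits the claim. Appendix C permits 'Unlikely'; it does not force it. But the heading over 'Possibly' says that two criteria must be met, and row 2 meets one. No sentence says which text prevails when they differ.

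Safeguards exist but do not settle the matter. The Medical Monitor reviews causality, but no reference text is named for that review. The rule favouring the more conservative assessment needs a disagreement and concerns reportability, not the tables. Counting missing causality as related does not help an event already coded 'Unlikely'. Listings show the Sponsor's causality, except for patients enrolled under the previous sponsor.

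It is also fair to say that some events in row 2 would not conflict. If the investigator finds the alternative clear, or the drug link non-plausible, 7.8 itself gives 'Not related'. Neither document defines the line between a ready and a clear explanation.

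Three stronger readings are tempting and unsupported:

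- **That the related-AE rate will be understated.** The documents give no basis for counting affected events, so no effect on the rate can be claimed.
- **That dose finding is compromised.** Section 7.8 refers DLT attribution to 7.7.3, which has its own test.
- **That errors run equally in the other direction.** With improbable timing, no ready disease explanation and a known pattern, Appendix C scores 2 of 3 for 'Possibly'. But 7.8's 'Unlikely' also speaks of plausible alternative explanations, so its answer for that event is arguable. This case should not be relied on.

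**Conclusion.** The conflict is real and the wording should be corrected. For a well-timed event that disease could readily but not clearly explain, that is not judged non-plausible and that has no known drug pattern, 7.8 gives 'Possibly related'. Appendix C's counts deny that category and allow 'Unlikely'. The event can then leave the related-AE outputs through a stated rule, not through a difference of clinical opinion.

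The consequence is bounded. It concerns the related flag and the outputs built on it. Total AE counts, all-causality tables and DLT decisions are unaffected, and all safety analyses are descriptive. The conclusion assumes that at least some assessors apply the Appendix C counts as written, and that the profile occurs. Both are plausible, but neither can be shown from the documents.

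**What to change.** 1. Add one sentence to Protocol 7.8, to Appendix C, and to SAP 7.2.2 at its Appendix C reference: *where the two differ, the Section 7.8 definitions determine the causality category that is coded and used in the related-AE tables.*
2. Delete the required counts for 'Unlikely' and 'Possibly' in Appendix C, or replace those two rows with the 7.8 wording and no counts. Adding a timing condition while keeping the counts would not be enough. An event with improbable timing, no ready disease explanation and a known pattern would fail 'Possibly' on timing and score only 1 of 4 for 'Unlikely', so neither category would fit.
3. Within the existing Medical Monitor review, before database lock, check well-timed events coded 'Unlikely' against 7.8.

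The cost is a wording amendment to the protocol, one sentence in the SAP, and a targeted check inside a review that already takes place. The reported related-AE rate may be slightly higher as a result. The causality definitions in SAP 7.2.2 need no change.
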